teams or act as voluntary responders to announced mock codes will be eligible to participate. The number of on-site participants for each simulated IHCA event is expected to average 15-25.

- Telemedical intensivist IHCA copilot: Board-certified or board-eligible critical care medicine physicians on the staff of the Intermountain Healthcare Telecritical Care Center will act as IHCA team copilot. The total number of expected participants is up to 30.

Recruitment:

- Local IHCA team: IHCA team activation will employ the participating hospital's standard mechanism. A sign posted outside the room used for the mock code will indicate that a video-recorded simulation is taking place. After completion of the simulation, participants will receive an information sheet about the study.
- Telemedical intensivist IHCA copilot: Eligible telemedical intensivists will be invited to participate by email and in person.

Methods/Procedures:

- Study design: Randomized, multicenter, simulation-based clinical trial
- Intervention: Standardized consultation to IHCA team by off-site intensivist via two-way audiovisual link using a mobile telemedicine cart
- Control: Display of silent, pre-recorded, non-interactive videotape of an ICU physician. The on-site participants will be told that an intensive care physician is observing the mock code.
- Randomization: Each event will be randomly assigned to intervention or control using block randomization by hospital.
- Procedures:
 - All event will be randomly pre-assigned to intervention (participation via telemedicine link by a remote critical care physician) or control (prerecorded video of telemedicine physician displayed on mobile telemedicine cart).
 - A research coordinator will arrange a time for mock code with local hospital clinical leadership and Code Blue leadership. The remainder of the IHCA team will not be informed that the announced event is a simulation prior to team activation.
 - The research coordinator and an experienced simulation technician will set up simulation equipment in an unused patient care room on the general medical or surgical ward at the hospital, including video recording device and mobile telemedicine cart.
 - Research coordinator will obtain final confirmation with the on duty clinical leadership that simulation will not interfere with patient care.
 - The hospital's on duty IHCA resuscitation team will then be activated via the hospital's standard mechanism.

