- Mock codes terminated in progress due to competing clinical priorities prior to simulated return of spontaneous circulation will be excluded from the final analysis. If this occurs, the simulation event may be rescheduled at the same hospital for a later date, with the rescheduled mock code assigned to the same study arm as the aborted mock code.
- If systematic problems interfering with study implementation, data collection, or interpretation are identified after study initiation, the study may be halted temporarily while the systematic issues are addressed. Affected events where data is invalid will be considered part of a roll-in phase of the study and will be excluded from data analysis. For each assigned to roll-in event status, we will schedule a make-up event at the affected hospital. Make-up events will be assigned to the same study arm as the roll-in event being replaced and will be interposed randomly with other events at the affected study site.
- Data collection: A research coordinator will be present at all mock codes. Besides study implementation duties, the coordinator will record team composition and function, processes of care, and leadership behaviors. Additional data will be obtained from (1) the simulator device, (2) the defibrillator device, (3) videotaped recording obtained via the mobile telemedicine carts, and (4) a brief questionnaire completed by IHCA team members upon completion of the mock code.
- The primary outcome for the study will be the fraction of time between activation of the telemedicine cart and beginning of the pulse check following the subsequent second full cycle of CPR that the IHCA team does not deliver chest compressions (“no-flow fraction”). Secondary outcomes are shown in Table 1.
 - On-site IHCA team members will complete a brief questionnaire (attached) to measure the subjective experience of individual and team function and — when applicable,

[figure not shown]

Figure 1. Unified structure for mock code scenarios. (ROSC: return of spontaneous circulation.)

opinions about the simulated mock code. Some on-site study participants will also complete a short-form version of the State-Trait Anxiety Index (STAI)¹⁶ validated for measurement of state anxiety (i.e. anxiety/stress at the time the questions are answered).¹⁷ Some participants may complete the survey online using REDCap, a secure web application for building and managing online surveys and databases.¹⁸

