Fraction of chest compressions with incomplete release*	Simulator mannequin	Defibrillator
Fraction of 30s segments with 8-12 breaths/minute^{23*}	Simulator mannequin	Defibrillator
Fraction chest compressions at target rate (100-120/minute)*	Simulator mannequin	Defibrillator
Time to first dose of epinephrine	In-person observation	Video recording
ACLS protocol adherence fraction (using validated instrument)	In-person observation	Video recording

ACLS protocol errors of commission, timing and omission ²⁴	In-person observation	Video recording
Team Emergency Assessment Measure (TEAM) score ²⁰	In-person observation	Video recording
Number and types of input by telemedical intensivist copilot	Video recording	In-person observation
On-site provider experience during mock-code	Questionnaire	
On-site provider satisfaction with telemedical intensivist copilot	Questionnaire	
On-site provider short-form State-Trait Anxiety Inventory score ^{16,17}	Questionnaire	
Off-site copilot experience during mock code	Questionnaire	Qualitative interview
Audiovisual connection or equipment problems (logistic or technical)	In-person observation	Questionnaire

* Outcome measured over (1) primary analysis window and from (2) activation of telemedicine cart; (3) "Code Blue" activation; and (4) from arrival of first resuscitation team member until simulation termination

Data analysis:

The primary analysis will include completed simulation where CPR quality data is complete and non-corrupted. Simulations for which equipment malfunction preclude measurement of compression quality will be excluded from analysis. Simulation events where malfunction of audiovisual recording equipment or major deviations during simulation implementation prevent accurate evaluation of resuscitation team performance and protocol will be excluded from analyses addressing these topics. Prematurely terminated simulation events and simulation events classified as run-in events will be excluded from all analyses.

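### Randomised events that have already been run can be reclassified as roll-in and dropped from every analysis, by a decision that need not be blind; this can bias the primary comparison

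*Combined protocol and SAP*

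**What the plan says.** Under Methods/Procedures, Randomization: "Each event will be randomly assigned to intervention or control using block randomization by hospital". Assignment comes before the event, so any event that has been run is a randomised event.

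The roll-in rule is in the Procedures list of the same section. It begins "If systematic problems interfering with study implementation, data collection, or interpretation are identified after study initiation, the study may be halted temporarily" and goes on: "Affected events where data is invalid will be considered part of a roll-in phase of the study and will be excluded from data analysis". Each such event gets a make-up at the same hospital: "Make-up events will be assigned to the same study arm as the roll-in event being replaced and will be interposed randomly with other events".

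The Data analysis section sets four rules that meet this one:

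- The primary analysis takes completed simulations whose CPR quality data are intact.
- "Simulations for which equipment malfunction preclude measurement of compression quality will be excluded from analysis".
- A recording failure or a major departure in how the simulation was run removes an event only from the analyses of team performance and protocol that it spoils.
- "Prematurely terminated simulation events and simulation events classified as run-in events will be excluded from all analyses".

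The plan does not define a systematic problem or invalid data, say who decides, require the decision to be blind to arm or result, or plan any analysis that keeps these events. The coordinator, who is at every event, switches on either the live link or the control video and so knows the arm. Both arms use the telemedicine cart; the control arm shows a recording on it. Table 1 lists connection and equipment problems among the secondary outcomes.

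**The concern.** The rule lets the analysis set be settled after events have been run, on the strength of what happened in them. For the primary outcome, events without a usable compression record are already excluded by the Data analysis section. What the roll-in rule can add is events whose compression data exist but which are judged invalid for another reason.

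Two things are at stake. First, if copilot events with a failed link or failed delivery are relabelled, the comparison drifts from the copilot strategy as randomised towards the copilot when the link works, and information on a listed secondary outcome is lost. Second, if the person deciding knows the no-flow result, poor results can be removed, even without intent. Same-arm make-ups restore the count in each arm but not the comparison: the events removed were selected, and their replacements inherit an arm and take place later.

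**Working it through.** **Step 1. Set the rules side by side, for the primary analysis.**

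| Event | Not labelled roll-in | Labelled roll-in |
|---|---|---|
| Compression record unusable | out | out |
| Compression record usable, major departure in running the simulation | in | out |
| Compression record usable, link or copilot delivery failed | in | out |
| Compression record intact, but a scenario or timing fault spoils the measurement window | not addressed | out |

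The label changes nothing in the first row. In the second and third it removes a measurable primary outcome. In the fourth it does legitimate work, because the primary window runs from cart activation to the pulse check after the second full CPR cycle and can be spoiled without any device fault.

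**Step 2. Inputs.** From the power analysis: control mean 0.285, target decrease 0.09, 38 events per arm, 80% power. From Data analysis: two-sided unequal-variance t-test. Not stated: alpha (assumed 0.05) and SD.

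**Step 3. Back-solve the SD.** The 38 per arm cannot be reproduced without an SD, so solve for it: SD = 0.09 × √(n/2) / (1.960 + 0.842).

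- 38 analysed per arm: 0.09 × √19 / 2.802 = 0.140 (0.138 with the t distribution).
- About 32 analysed per arm after the 15% loss (38 × 0.85 = 32.3): 0.09 × √16 / 2.802 = 0.1285.

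The documents do not settle which applies. Both were used below.

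**Step 4. Type I error when copilot events are relabelled.** Simulation with no true effect: normal outcomes, mean 0.285 in both arms, 38 per arm, 40,000 trials per setting. Each copilot event gets a score ρ × (y − 0.285)/SD + √(1 − ρ²) × noise. The k events with the highest scores are replaced by fresh draws from the same arm, and the Welch test is run at 0.05. Here ρ = 0 means relabelling unrelated to outcome, and ρ = 1 means the worst k results are always the ones replaced. With SD 0.14:

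| k of 38 | ρ = 0: bias, type I error | ρ = 0.5 | ρ = 1 |
|---|---|---|---|
| 2 | 0.000, 5.1% | −0.007, 5.7% | −0.015, 8.4% |
| 4 | 0.000, 4.9% | −0.012, 6.9% | −0.025, 14.0% |
| 6 | 0.000, 5.0% | −0.016, 8.3% | −0.033, 20.4% |

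The Monte Carlo standard error near 5% is √(0.05 × 0.95 / 40,000) = 0.1 percentage points. SD 0.1285 gives nearly the same: 5.6% and 6.9% at ρ = 0.5, and 8.2% and 13.8% at ρ = 1, for k = 2 and 4. As a check, bias should be proportional to ρ, and the ρ = 0.5 column is half the ρ = 1 column.

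Replacing the worst four in both arms leaves the difference at about 0 but gives type I error of 7.8%. Blinding to arm alone would therefore not be enough.

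**Step 5. Drift when the copilot works.** Suppose a fraction f of copilot events gains nothing because the link failed. The as-randomised effect is 0.09 × (1 − f): 0.0855 at f = 0.05 and 0.0765 at f = 0.15. If every such event were replaced, the trial would report 0.09, an overstatement of 0.09/0.0855 − 1 = 5% to 0.09/0.0765 − 1 = 18%. Both values of f are assumptions, and replacing every such event is the extreme case.

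**The case against.** The rule has limits of its own. The problem must be systematic, and only affected events with invalid data are reclassified. A single dropped link is not obviously systematic and does not spoil a mannequin record. The Data analysis section also keeps events with major departures in the primary analysis if their compression data are intact. The primary outcome is measured by a device. Nothing says that the coordinator decides roll-in status or sees no-flow results first. The worst-case figures describe someone picking out the worst results in one arm, which the rule does not tell anyone to do.

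Most of this stands, and it rules out three stronger readings that a reader might infer:

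- *The problems arise mainly in the copilot arm.* The documents give no rates by arm. The cart and the mannequin serve both arms, and the trigger also covers data-collection faults. Only the live link and the live intensivist are specific to one arm.
- *The rule biases the result.* It can do so only if relabelling is related to outcome or to copilot delivery; otherwise type I error stays near 5%.
- *The rule adds nothing but discretionary exclusions.* A scenario or timing fault can invalidate the no-flow fraction without equipment malfunction.

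The objection does not remove the gap. Invalid is not tied to the primary outcome record, so the roll-in label can override the narrower rule for major departures. Device measurement limits biased measurement, not biased exclusion.

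**Conclusion.** The concern holds as a risk, and the plan should be changed. Events already randomised and run can leave the primary analysis although their outcome is measurable, through a decision that need not be blind, and no analysis shows what difference this made. A copilot-only route to exclusion exists, so the arms may be affected differently.

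The size depends on how the rule is used. It is nil if relabelling is unrelated to outcome. For two to four of 38 copilot events replaced under no true effect, type I error is about 5.7% to 6.9% with moderate selection and about 8% to 14% at worst, with bias of up to 0.025 in the worst case against a target of 0.09. These figures rest on alpha 0.05, an SD of about 0.14, normal outcomes and assumed numbers relabelled, none of which the documents state.

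**What to change.** - For the primary outcome, exclude a roll-in event only if its no-flow fraction cannot be validly measured: an unusable compression record, or a scenario or timing fault that invalidates the measurement window.
- Have an existing team member who sees neither arm nor no-flow result make and log that judgement, with the reason.
- Keep events with link or copilot-delivery failure and usable compression data in their assigned arm.
- Report roll-in events by arm with reasons.
- Add a sensitivity analysis of the primary outcome with every randomised, completed event that has usable compression data, roll-in events included. State in advance whether the make-up for a retained event also counts.
- Use one term, roll-in or run-in, throughout.

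A calendar cut-off that discards all events at an affected hospital is not needed, and it would throw away valid randomised data.

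The cost is protocol wording and one extra analysis. The downside is some dilution of the estimated effect by events with technical failure, of the order shown in Step 5 if failures are as frequent as assumed there.

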- Off-site IHCA team copilots will complete a brief questionnaire (attached). Most participants may complete the survey online using a version of this questionnaire implemented in REDCap.¹⁸ Opinions about the procedure will also be elicited through post-study qualitative interviews.
- ACLS protocol adherence and violations using a checklist adapted from previously validated research tools.^{8,40}
- Leadership behaviors will be evaluated according to a previously published taxonomy.¹⁹
- Overall function of the IHCA team will also be evaluated using a previously validated instrument.^{20,21}
- Number of simulation events and power analysis: Assuming a baseline no-flow percentage of 0.285,^{10,22} a best-case no-flow fraction of 0.08 (protocol guidelines advise a single 10 second pause in chest compressions for a pulse and cardiac rhythm check every two minutes), and equipment malfunction or simulation termination precluding event analysis for 15% of mock codes, we will require 76 completed mock codes (38 in each arm) to achieve 80% power to detect a 31% relative decrease (9% absolute decrease) in the mean no-flow fraction.
- Study duration: The 76 planned mock codes will be divided between the 7-8 participating institutions. We expect to complete 2-6 simulations at each participating hospital every 2 months. Accounting for scheduling conflicts and expected intermissions during implementation of a new electronic medical record at some study hospitals, we expect study completion to require 18-24 months (and potentially up to 48 months) after simulations begin.

Informed consent (“copilot” physicians): Members of the research team will approach the eligible subjects by email (see attached) or in person at their workplace. Interested subjects will be consented by research team member(s) according to the Intermountain Healthcare Informed Consent Policy.

Table 1: Descriptive & outcome measures for randomized trial of telemedical intensivist IHCA team copilot

Variable	Data source	
	Primary	Secondary
Response team characteristics		
Response team structure	In-person observation	Video recording
Past experience of code team members	Questionnaire	
Primary outcome		
Fraction of pulseless time with no chest compressions*	Simulator mannequin	
Secondary outcomes		
Time from onset of shockable rhythm to defibrillation	Simulator mannequin	Defibrillator
Fraction of chest compressions in target depth range^{23*}	Simulator mannequin	Defibrillator

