Between-group comparisons for continuous variables will employ two-sided t-tests with unequal variance. Comparisons for binary or categorical variables will employ Fisher's exact test or chi-squared test as appropriate. Given clustering within simulations, between-group comparisons of survey responses will employ multilevel logistic (for binary variables) or linear (for continuous variables) regression with a random effect for simulation event. Comparisons of Likert-style variables will use the rank-sum method described Datta/Satten.²⁸

Sample size/power analysis: Assuming a baseline no-flow percentage of 0.285, a best-case no-flow fraction of 0.08 (protocol guidelines advise a single 10 second pause in chest compressions for a pulse and cardiac rhythm check every two minutes), and equipment malfunction or simulation termination precluding event analysis for 15% of mock codes, we will require 76 mock codes (38 in each arm) to achieve 80% power to detect a 31% relative decrease (9% absolute decrease) in the mean no-flow fraction. We therefore expect to enroll 1900 on-site IHCA team members as study subjects (although some participants may participate in >1 mock code).

Waiver of Informed Consent and HIPAA Authorization (for on-site IHCA team members):

We are requesting a waiver of informed consent and HIPAA authorization for on-site IHCA team study participants of this study. Participation in this study is similar to standard training for IHCA team members and involves no more than minimal risk to the subject. Individuals will be notified by means of a prominently displayed poster(s) that a simulation-based research project with video recording is in progress. Such notification will address individuals reasonable expectation of privacy. We will not use video recordings for any purposes except research, and digital video recordings will be stored securely and then transferred to a secure, approved server of the Intermountain network. We will not systematically collect individually identifiable information. The research therefore involves no more than minimal risk to the subjects; the only potential risk is a breach of confidentiality, and protections are in place to safeguard the data. Because risk is minimal, the waiver of consent and authorization will not adversely affect the rights or welfare of subjects.

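### Does counting the 76 mock codes as both completed and planned, with 15% unanalysable, undercut the stated 80% power?

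*Combined protocol and SAP*

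**What the plan says.** The sample size appears three times in the combined protocol and SAP.

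- Methods/Procedures, Number of simulation events and power analysis: "we will require 76 completed mock codes (38 in each arm) to achieve 80% power". The same sentence lists, as an assumption, "equipment malfunction or simulation termination precluding event analysis for 15% of mock codes".
- Methods/Procedures, Study duration, the next bullet: "The 76 planned mock codes will be divided between the 7-8 participating institutions".
- Data analysis, Sample size/power analysis: "we will require 76 mock codes (38 in each arm) to achieve 80% power", with the same 15% assumption, followed by "We therefore expect to enroll 1900 on-site IHCA team members as study subjects".

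The target effect is a "31% relative decrease (9% absolute decrease) in the mean no-flow fraction" from a baseline of 0.285. Continuous outcomes are compared with two-sided t-tests allowing unequal variances. Neither the standard deviation nor the alpha behind the calculation is given.

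The primary analysis takes completed simulations whose CPR quality data are intact. The Procedures list allows a terminated event to be rescheduled in the same arm. It commits to make-up events where a systematic problem has made data invalid (roll-in events). It has no replacement rule for an isolated equipment failure.

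**The concern.** With a 15% loss, the number run and the number usable differ by roughly a sixth. If 76 must be completed and usable, 76/0.85 = 89.4, so 90 would have to be run. If 76 are run, about 64 are usable. The plan attaches the same 80% power to 76 under both labels.

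Two things would be at stake. If the calculation needed 76 usable events and the team stopped after running 76, the trial would have less power than stated. If 76 already included the loss and the team held out for 76 completed, it could run up to 14 more simulations (90 − 76) than needed, each calling on a hospital's on-duty response team. With no standard deviation or alpha, a reader cannot recompute 76 to see which was meant.

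**Working it through.** **Inputs from the documents.** Baseline 0.285; difference 0.09 (0.09/0.285 = 31.6%, stated as 31%); power 80%; 38 per arm; loss 15%; two-sided t-test; 15 to 25 on-site participants per event.

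**Assumed, because not stated.** Two-sided alpha 0.05. The standard deviation (SD) is back-solved under each reading.

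**Can 76 be reproduced?** Not from the stated inputs alone. Treating the fractions as binary proportions (0.285 against 0.195) gives 353 per arm, so a comparison of means was evidently used, and that needs an SD. The loss arithmetic can be checked without one:

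- 64/(1 − 0.15) = 75.3, which rounds up to 76. An analysable total of 64 (32 per arm) inflates to the stated figure.
- 76/(1 − 0.15) = 89.4, which rounds up to 90. That number appears nowhere in the documents.

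**Implied SD.** With n per arm, SD = 0.09 / [(1.960 + 0.842) × √(2/n)].

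- 76 already includes the loss, n = 32: 0.09 / (2.802 × 0.250) = 0.1285 (noncentral t: 0.1265).
- 76 are needed for analysis, n = 38: 0.09 / (2.802 × 0.2294) = 0.140 (noncentral t: 0.138).

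**Power under each reading.** Power ≈ Φ(0.09 / [SD × √(2/n)] − 1.960). The noncentral t agrees with each result to within half a percentage point.

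| Analysable events needed for 80% | Implied SD (normal) | Power at 32 per arm | Power at 38 per arm |
|---|---|---|---|
| 64 | 0.1285 | 80% | 86% |
| 76 | 0.140 | 73% | 80% |

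In the second row, the difference detectable with 80% power at 76 × 0.85 / 2 = 32.3 per arm is about 0.09 × √(38/32.3) = 0.098, or 34% of 0.285.

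A one-sided alpha of 0.05 would move the 86% and 73% only to about 86% and 74%. Using 0.31 × 0.285 = 0.088 as the difference changes the implied SD but not these powers.

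The right-hand column is what 76 completed and analysable events deliver: 80% or 86%, never less. The only cell below 80% requires three things together: 76 analysable events are needed, only 76 are run, and no lost event is replaced.

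**Which reading does the text support?**

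- In both places the 15% loss is an input to the sentence that produces 76. If 76 were the count after losses, that input would do no work, and the sentence should have led on to 90.
- The Study duration bullet uses 76 as the number to schedule across hospitals.
- 1900/76 = 25 exactly, the top of the expected range per event. At 25 per event, 90 events would have given 2250.

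On the other side stands the single word completed in one of the two power statements.

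**The case for a change.** The strongest reply is that a protocol should not leave its event target to inference. Completed is current text, not a conversion fault, and it conflicts with the next bullet. Completed does not even mean analysable here, since a finished simulation can still lose its compression data. Rescheduling a terminated event is optional, and an isolated equipment failure has no replacement rule, so replacement cannot be relied on to restore the count. The 1900 figure is not conclusive either: 1900/90 = 21.1 per event also lies within 15 to 25. A team could stop at 76 run or continue to 76 completed and claim to have followed the plan.

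Much of this stands. The wording is inconsistent, and without the SD and alpha the 80% can be neither confirmed nor refuted. What does not stand is a demonstrated loss of power. Under the reading with most textual support, stopping at 76 run gives the stated 80%, and going on to 76 completed gives up to about 86%, so either stopping point is adequate. The full 15% shortfall is also a worst case, because roll-in events will be made up and terminated ones may be. The documents describe no interim comparison of the arms, so nothing in them would let the choice of stopping point depend on results.

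**Conclusion.** The concern does not call for a change. One power statement contains a stray word, and the calculation is reported without its SD and alpha. Read as 76 events run with about 64 analysable (32 per arm), the plan is coherent and its 80% power for a 0.09 difference stands, with an implied SD of about 0.127 (noncentral t) at a two-sided alpha of 0.05. If all 76 prove analysable, power is about 86%. The 73% figure rests on a combination that the documents do not state and that their own loss arithmetic argues against.

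The analysis is the same on either reading: same test, same analysis set, same allocation. Quoting the top of the participant range as the expected enrolment affects no result. The conclusion depends on the assumed alpha and back-solved SDs only for the exact powers. The point that 76 completed and analysable events cannot give less than the stated 80% holds under both readings of the plan's own calculation.

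### The exclusion rules in Data analysis also apply to the technical-problem outcome in Table 1, so its rate will not describe all mock codes started and may be too low

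*Combined protocol and SAP*

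**What the plan says.** Under secondary outcomes, Table 1 lists "Audiovisual connection or equipment problems (logistic or technical". In-person observation is its primary data source and the questionnaire its secondary source. The table also lists "On-site provider satisfaction with telemedical intensivist copilot", taken from the questionnaire.

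The Data analysis section has exclusions of different reach:

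- Widest: "Prematurely terminated simulation events and simulation events classified as run-in events will be excluded from all analyses".
- Equipment: "Simulations for which equipment malfunction preclude measurement of compression quality will be excluded from analysis". This has no stated scope, but it follows directly on "The primary analysis will include completed simulation where CPR quality data is complete and non-corrupted".
- Recording faults and major implementation deviations: these events "will be excluded from analyses addressing these topics", the topics being team performance and protocol.

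The Procedures list under Methods/Procedures explains the two classes in the widest rule. On early termination: "Mock codes terminated in progress due to competing clinical priorities prior to simulated return of spontaneous circulation will be excluded from the final analysis". On roll-in, after describing systematic problems with implementation, data collection or interpretation: "Affected events where data is invalid will be considered part of a roll-in phase of the study and will be excluded from data analysis". Each roll-in event gets a make-up event in the same arm. Procedures says roll-in and Data analysis says run-in; I take them to be the same class.

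Neither section exempts the technical-problem outcome or says that problems in excluded events will be tabulated.

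**The concern.** The reason for excluding an event overlaps with what the outcome counts. A systematic fault in the equipment or the connection is an obvious way for an event to become roll-in. Once it does, the event disappears from the technical-problem outcome, and its replacement will probably be run after the fault has been dealt with. If the equipment exclusion is read broadly, the same holds for a mannequin failure that destroys the compression data.

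This outcome is the table's direct measure of whether the equipment and the link work. A reader will take the rate as the share of attempted mock codes with a problem. Computed under the written rules, it is the share among events that survived the exclusions. The primary comparison is a separate matter and is not in question here.

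**Working it through.** **Step 1. Which events stay in the technical-problem outcome, as written?**

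| Type of event | Rule | Counted? |
|---|---|---|
| Roll-in (run-in) event | Out of all analyses | No |
| Event stopped early | Out of all analyses | No, but the stated reason is competing clinical priorities |
| Compression data lost to equipment malfunction | Out of analysis, scope not given | Unclear |
| Recording fault or major deviation | Out of team-performance and protocol analyses only | Yes |
| Failed link, event completed, CPR data valid | No exclusion named | Yes |

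The gap is therefore certain for roll-in events and possible for compression-equipment failures. It does not extend to every technical fault.

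**Step 2. How far could the rate move?** The plan gives no expected rate for this outcome, so there is no stated figure to reproduce. The sample size section supplies two inputs: 76 mock codes, and 15% unanalysable through equipment malfunction or termination. The other two inputs are assumptions: p, the problem rate among analysed events, and f, the share of excluded events that had a technical problem.

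- Excluded: 76 × 0.15 = 11.4, taken as 11. Analysed: 76 − 11 = 65.
- Rate over all events: R = (65p + 11f) / 76.
- Shift from the reported rate: R − p = 11(f − p) / 76.

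| p (reported) | f = 0 | f = 0.25 | f = 0.5 | f = 1 |
|---|---|---|---|---|
| 0% | 0.0% | 3.6% | 7.2% | 14.5% |
| 5% | 4.3% | 7.9% | 11.5% | 18.8% |
| 10% | 8.6% | 12.2% | 15.8% | 23.0% |
| 20% | 17.1% | 20.7% | 24.3% | 31.6% |

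For p = 10%: (6.5 + 0)/76 = 8.6% at one end and (6.5 + 11)/76 = 23.0% at the other. The reported rate is too low whenever f exceeds p and slightly too high when f is below p.

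**Step 3. Other reading of 76.** The section on the number of simulation events calls the 76 completed mock codes. Then 76/0.85 = 89.4, so about 90 are started and 14 lost. For p = 10% the range is (7.6 + 0)/90 = 8.4% to (7.6 + 14)/90 = 24.0%, almost the same.

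**Step 4. What the range leaves open.** The 15% is not split between malfunction and termination. Steps 2 and 3 treat the whole of it as lost to this outcome, which needs the broad reading of the equipment exclusion; on the narrow reading only the terminated part is lost. The 15% also does not mention roll-in. Roll-in losses may come on top, and each one with a technical fault would add one event to both numerator and denominator. The documents give no number for them.

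**The case against.** The best reply is that the exclusions are tiered and most technical faults survive them. That stands. Recording failures leave only the team-performance and protocol analyses. A dropped link in a completed event with valid CPR data is kept and counted. Early termination is tied to patient-care needs, so those events need not be technical failures. The equipment sentence comes straight after one defining the primary analysis and may well have been meant for CPR-quality data only. A mannequin fault also says little about the telemedicine link.

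A reader might infer that every event with a technical failure drops out of every analysis, or that the exclusion criterion and the outcome are the same thing. The tiers contradict the first. As to the second, roll-in status requires a systematic problem and invalid data, and the problem may lie in implementation, data collection or interpretation. That overlaps with the Table 1 item but is not identical to it.

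A reader might also infer that satisfaction with the copilot is biased upward. Nothing in the documents links exclusion to lower satisfaction, events stopped for patient care may yield few questionnaires, and copilot experience also draws on post-study interviews that are not tied to single events.

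The reply does not remove the core point: roll-in events leave all analyses without exception, and no passage restores them to an outcome that their problems may belong to.

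**Conclusion.** The point holds in a limited form. As written, the technical-problem outcome omits roll-in and early-terminated events, and perhaps those with compression-equipment failure. Its rate will not describe all attempted mock codes and may be understated.

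The size is a range and not an estimate. An observed 10% would correspond to about 9% to 23% over all 76 events. This rests on the planned 15% loss, the assumed 10%, an unknown share of technical faults among the lost events, and the broad reading of the equipment exclusion. The low end shows that the rate could also be slightly overstated. Any effect on satisfaction is unknown in direction as well as size. This is a reporting gap in a secondary outcome that is worth closing, and the documents show no fault in the primary result from it.

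**What to change.** In Data analysis:

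1. Exempt the technical-problem outcome from the exclusions. Compute it on every mock code that was started, by arm, including aborted, equipment-failure and roll-in events. Show each event's fate and exclusion reason, and identify make-up events.
2. State that the exclusion for lost compression data applies only to CPR-quality analyses.
3. Use one term for roll-in and run-in events.
4. Add a sensitivity analysis of satisfaction and experience that includes questionnaires returned from excluded events. The retained events can remain the main set, since roll-in events may reflect an implementation fault since corrected.

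This takes a few sentences and no new data collection: a research coordinator attends every mock code, and in-person observation is already the primary source for this outcome. The primary analysis set is unchanged. The price is a possibly less favourable technical-problem figure and some questionnaires from incomplete events.
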